## 2. STUDY OBJECTIVES, DESIGNS AND ENDPOINTS

### 2.1 Study Objectives

**Primary objective:** To demonstrate the safety of the Control-IQ 2.0 System for the management of type 1 diabetes by assessing rates of AEs after using new features.

**Secondary objective:** To further assess the safety of new features that potentially will be added to the current Control-IQ System; specifically, improved time in range 70-180 mg/dL, improved time in the tight glycemic range 70-140 mg/dL, and lower median glucose, with no increase in time <54 mg/dL.

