Sites visits may be remote if updating of pump firmware is not required at the visit, per investigator discretion.

316

Confidential

Contains trade secrets and/or confidential information exempt from disclosure from 21 CFR 20.61

**Baseline Data Collection:** Only Control-IQ users demonstrating use of Control-IQ in closed-loop at least 80% of the time during the 2 weeks before enrollment are eligible for the study. Data from the 2-week period before enrollment will serve as the baseline pump and CGM data.

**Subject Completion or Early Withdrawal:** The subject completes the study approximately 5 weeks after enrollment, or when they choose to withdraw from the study, if earlier than 5 weeks.

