## **4.5 Study Procedures**

### **4.5.1 Phase 1: 48-hr supervised study in-clinic/transitional environment:**

Approximately 5 subjects will be enrolled in Phase 1 of the study. The purpose of Phase 1 is to determine the safety of the Control-IQ Pro v2.0 system with use of the new features in a medically supervised, observed setting: 1) Lower target normal activity overnight and receiving auto-correction boluses, 2) Exercise Activity without autocorrections, and 3) Adjustments to meal bolusing.

After enrollment and collection of baseline data (use of the current standard Control-IQ commercial system for 1-3 weeks) subjects will be admitted in the evening and will switch from their personal t:slim X2 insulin pump with Control-IQ technology to the t:slim X2 study pump with Control-IQ Pro v2.0. Subjects will receive training on all of the new features and the instructions for using them during the ~48-hours of the study.

During this phase of the study, subjects will be remotely monitored by the study team, including a study physician, 24 hr per day. Pump and CGM alerts will be set to annunciate throughout the study. The study team will intervene if 1) CGM <70 mg/dL overnight, or 2) if a Control-IQ Low Alert occurs (indicating that the glucose is predicted to fall below 70 mg/dL within 15 minutes). Meal boluses will be supervised by study staff to ensure that the correct number of carbohydrate grams are entered into the bolus calculator.

At least one member of the study medical staff (Physician, NP) from will be present on site at all times. Up to 5 subjects will be studied at one time during the supervised phase. The goal of this

phase is to evaluate the safety of the system with correct and incorrect use of new features of the system.

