#### **4.5.2 Phase 2: At-home study**

After enrollment and collection of baseline data, subjects will switch from their personal t:slim X2 insulin pump with Control-IQ technology to the t:slim X2 study pump with Control-IQ Pro v2.0. Subjects will receive training on all of the new features and the instructions for using them during the following week of the study. Subjects will keep a log of their use of the required features of the new pump for the week. Subjects will be required to attend the study site visit each week (+/- 3 days), during which time their pump and CGM data will be downloaded and they will receive instructions for the following week.

Remote real-time monitoring using the Dexcom G6 app will be required to be shared by subjects with their local contact(s) throughout the study, and with study staff for the first 10 subjects. After the first 10 subjects complete the study, required real-time alerts to study providers may be removed for future subjects after sponsor review and approval. This review will certify that:

- 1) No severe hypoglycemia events related to algorithm delivered automated insulin dosing occur that required study staff intervention because the subject was not aware/treating appropriately in the first 10 subjects.
- 2) No severe hyperglycemic events related to algorithm delivered automated insulin dosing occurred that required study staff intervention because the subject was not aware/treating appropriately in the first 10 subjects.

During the weekly required visit, the Control-IQ software in their pump will be reconfigured to support the following week's features. The configuration tool will be run by clinical staff from an approved study laptop, using Bluetooth to reconfigure the pump. If a software update to the pump is not required at the weekly visit, and the subject is able to download their pump remotely, the visit may be performed remotely per investigator discretion.

After each weekly download, staff will review the download to document correct use of each feature, and document this on the study CRF. If a subject is using a feature not per the study instructions (for example, using eating soon not just prior to meals), subjects will be re-educated

on the relevant instructions and this will be documented in the study CRF. All subjects will receive a phone call 48 hours (+/- 1 day) after each weekly feature update to review any new questions that may arise.

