The feature use will be randomized per subject. The feature schedule is outlined below in **Table 4**:

**Table 4:** Schedule of prescribed use of standard vs. new features.

*Participants will be sorted into cohorts. Each cohort will be randomly assigned the order in which they complete weeks A-D.*

| Study Period                        | Normal Activity Setting                             | Exercise Setting                              | Eating Soon  | Late Meal Bolus     |
|-------------------------------------|---|---|--|---------------------|
| Baseline                     | Standard  | Standard                                      | N/A  | N/A                 |
| 2-day Supervised/Hotel Study | Lower Target
Auto-bolus on
Use while sleeping | Auto-Bolus Off x 2 required exercise sessions | Use once ~1 hour to meal

Use once for 3 consecutive hours prior to a meal | One time            |
| Week A                       | Lower Target
Auto-bolus on                       | Auto-bolus off                                | 40-60 minutes before every meal  | Directed not to use |
| Week B                       | Lower Target
Auto-bolus off                      | Auto-bolus off                                | 40-60 minutes before every meal  | Directed not to use |
| Week C                       | Lower Target
Auto-bolus on                       | Auto-bolus off                                | As needed  | As needed           |
| Week D                       | Standard Target
Auto-bolus on                    | Auto-bolus off                                | As needed  | As needed           |

Prior to sending any subject home with the study device, study staff will assure the following safety instructions are reviewed with subjects as part of device training:

- 1) Completion of the study device training form, reviewing the new features of Control-IQ 2.0 and their required use.
- 2) Study subjects will be given a logbook to record use of the late bolus feature, to record the time they ate their meal relative to pressing the late bolus feature button, as well as to record start and end of exercise.

- 3) Subject will be asked to set-up/re-enable sleep schedules after lunch if they desire, or may continue to use the normal activity setting overnight with the required targets per each week of the study.

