## 5. STATISTICAL CONSIDERATIONS

### 5.1 Statistical Analysis:

This feasibility study is a prospective, crossover 5-week home study with sequential interventions (new features). Each subject will use all features (current and new) and therefore will act as his/her own comparator (paired data points). The study is designed to obtain a primary safety profile on new feature configuration

Descriptive statistics of the rates of significant hypoglycemia (< 54 mg/dl), severe hypoglycemia, DKA, and serious adverse events will be reported for baseline and each intervention configuration. Additionally, descriptive statistics of glycemic outcomes will for baseline and each intervention configuration will be provided. The statistics will include:

- % time < 54 mg/dl median and interquartile range
- Number of events of severe hypoglycemia (needing assistance) and percent of individuals experiencing at least one event of severe hypoglycemia.
- Number of events of DKA and percent of individuals experiencing at least one DKA event.
- Rate of serious adverse events per 100 patient years.
- % time < 70 mg/d median and interquartile range
- % time > 250 mg/dl median and interquartile range
- % time between 70-180 mg/dl median and interquartile range
- % time between 70-140 mg/dL median and interquartile range
- Post-prandial glycemic peak median and interquartile range
- 4-hour post-meal glucose AUC median and interquartile range
- Median sensor glucose and interquartile range
- % time in automation median and interquartile range

These statistics will be calculated at the patient-level, and a sub-analysis of daytime vs. nighttime statistics will be provided.

Additionally, the distributions of glycemic outcomes for baseline and each intervention configuration will be depicted using boxplots. The individual-level difference between each intervention configuration and baseline will also be depicted using boxplots.

**Success Criteria / Goal:** The 48 hour observed session will be considered useful for data analysis if the subject has at least 75% CGM availability during the session.

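### Section 5.1 compares the median % time <54 mg/dL of a 14-day baseline with that of 7-day configuration weeks; if time <54 is sparse, the shorter window tends to give a lower median with no true effect

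*Combined protocol and SAP*

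**What the plan says.** - **Endpoint and statistic.** Time <54 mg/dL is the first primary safety endpoint (Section 2.3). Section 5.1 summarises it as "time < 54 mg/dl median and interquartile range" for baseline and each configuration, with no mean listed for any glycemic outcome. It adds that "These statistics will be calculated at the patient-level", so each subject contributes one value per period.
- **Paired display.** "The individual-level difference between each intervention configuration and baseline will also be depicted using boxplots" (Section 5.1).
- **Baseline window.** "Data from the 2-week period before enrollment will serve as the baseline pump and CGM data" (Section 4.4). For Phase 1 subjects, Section 4.5.1 describes baseline as "use of the current standard Control-IQ commercial system for 1-3 weeks".
- **Configuration window.** One week each: "Each cohort will be randomly assigned the order in which they complete weeks A-D" (Section 4.5.2, Table 4). The length is only nominal: "Subjects will be required to attend the study site visit each week (+/- 3 days".
- **Goal.** The secondary objective in Section 2.1 seeks better glucose control "with no increase in time <54 mg/dL". No margin, test or expected rate is given.

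Nothing in Section 5.1 puts the baseline and configuration summaries on windows of equal length.

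**The concern.** A subject observed for 7 days is more likely to show no time <54 at all than the same subject observed for 14 days. More zeros pull the across-subject median down, although the average percentage of time is unchanged. Where time <54 is uncommon, a configuration week can therefore show a lower median than baseline with no change in hypoglycemia, and a modest real increase can be partly masked.

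The baseline comparison carries weight. Baseline is the only period in Table 4 on the existing system throughout, and the only comparator for which Section 5.1 specifies individual differences. The synopsis says the results will help choose the feature set for later trials.

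**Working it through.** The plan states no figure for time <54, so there is none to reproduce. The check asks what the planned statistic does when nothing changes.

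**Inputs from the documents.** Baseline 14 days (Section 4.4); configuration 7 days (Section 4.5.2); up to 30 device users (Section 2.2); median across subjects (Section 5.1).

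**Assumptions.** Each subject's episodes <54 are Poisson. The weekly rate varies between subjects as a gamma distribution with shape *k* and mean *m*. Episodes average 25 minutes (gamma, CV 0.8). A week has 7 × 24 × 60 = 10,080 minutes, so mean % time <54 = *m* × 25 / 10,080. For *m* = 1 this is 0.25%.

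**Step 1: share of subjects with no time <54.** Over *w* weeks the share is (k / (k + w·m))^k. With k = 1 and m = 1:
- 7 days: 1 / (1 + 1) = 0.50
- 14 days: 1 / (1 + 2) = 0.33

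Without between-subject variation the shares are exp(−1) = 0.368 and exp(−2) = 0.135. Either way, the shorter window has more zeros.

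**Step 2: expected median of 30 subjects, no true effect, k = 1** (6,000 simulated trials per row).

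| Episodes/week | Mean % time <54, both windows | Median, 14 days | Median, 7 days |
|---|---|---|---|
| 0.7 | 0.17 | 0.07 | 0.01 |
| 1.0 | 0.25 | 0.130 | 0.056 |
| 1.5 | 0.37 | 0.22 | 0.16 |
| 2.5 | 0.62 | 0.40 | 0.35 |

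At a mean of 0.25% the study-week median is below the baseline median in 83% of trials. At means of 1.2% and 2.5% the 7-day median is only about 4% and 2% lower.

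**Step 3: a different episode model.** Here each episode lasts 15 minutes plus an exponential time averaging 10 minutes. Runs were made without between-subject variation, with it, and with day-level clustering added. With no effect, the expected 7-day median was lower in all 18 scenarios: by 14-52% at a mean of 0.25%, 9-25% at 0.37%, 6-17% at 0.5%, 3-11% at 1.0% and 1-8% at 2.5%. The direction is stable; the size depends on the rate and on clustering.

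**Step 4: paired differences (Step 2 model, mean 0.25%).** The expected median of configuration minus baseline is about −0.01 percentage points for k = 1 and −0.02 for k = 2. The unpaired gap at k = 1 is 0.056 − 0.130 = −0.074. The mean paired difference is zero apart from simulation error.

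**Step 5: equal windows.** With a 7-day baseline and no effect, the Step 3 model gives medians of 0.190 vs 0.191, 0.093 vs 0.093 and 0.066 vs 0.066 at a mean of 0.25%. The chance of a lower study-week median drops from 0.62-0.75 to 0.30-0.41. The artefact disappears.

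**The case against.** **The rate is unknown.** The documents never give time <54, and at about 1% or more the gap is mostly small. This stands: the point is conditional. A reader might infer that the median must fall in the study weeks, and the documents do not support that. They make sparseness plausible: Section 3.1 requires experienced users with at least 80% closed-loop use and at least 50% time in range, and Section 1.2 says the current system reduces time <70.

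**The paired boxplots already protect the comparison.** Largely true. A reader might infer that they carry the full bias; Step 4 shows only a fraction of it. But the tabulated medians are unpaired summaries and have no such protection.

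**The upper part of the distribution does not look better.** True. At a mean of 0.25% (k = 1), the 75th percentile is almost unchanged (about 0.36 in both windows) and the 90th is higher in the 7-day week (0.73 vs 0.65). The artefact concerns the median.

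**Severe hypoglycemia and DKA counts.** A reader might extend the point to these. That fails: Section 3.1.2 excludes anyone with either event in the past 6 months, so baseline counts are zero by eligibility whatever the window length.

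**Weeks A-D are nominally equal.** True, and C versus D isolates the lower target without a window difference. It does not replace the comparison with the existing system, because every week from A to D includes new features.

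**Small numbers matter as much.** Also true. In the Step 3 model at 0.25%, with a true 1.5-fold increase, the chance that the study-week median is not higher is 0.16-0.41 with a 14-day baseline and still 0.13-0.31 with a 7-day one.

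**Conclusion.** The concern holds in a limited form. The 14-day versus 7-day mismatch is in the plan. For a sparse, right-skewed time <54 it tends to lower the configuration-week median relative to baseline with no true effect. Under the assumed model the medians are about 0.07% vs 0.01% at a mean of 0.17% and 0.40% vs 0.35% at a mean of 0.62%, with equal means. The gap is about 2-4% at a mean of 1.2% or more (up to 11% at 1.0% with day-level clustering), and there is none where both medians are zero.

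The baseline length is itself unsettled. If 1-3 weeks were used, the mismatch would vanish at one week and grow at three.

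Two further inferences go beyond the evidence. The same distortion in time <70 and time >250 was not computed, and neither need be sparse in subjects admitted with time in range as low as 50%. Nor can one state how large a true increase would be hidden, because that depends heavily on the unknown rate and its variation.

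This should be fixed but is not critical: the study is descriptive, sets no test or margin on time <54, and bases its overall stopping rules (Section 8.13) on clinical events, malfunctions and sponsor review.

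**What to change.** In Section 5.1, before analysis:

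1. State one baseline length and reconcile Section 4.4 with Section 4.5.1.
2. Compute the baseline % time <54 summary on 7-day windows: either summarise each baseline week separately and average the two summaries, or use the last 7 days.
3. Take the paired differences against a 7-day baseline in the same way, and say how configuration periods shortened or lengthened by the visit tolerance are cut to a comparable window.
4. Report the mean and the mean paired difference beside the median and IQR, since the mean does not depend on window length.

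The cost is one paragraph and a few lines of code, with no new data. The downside is slightly noisier baseline values per subject. The change removes the window artefact but not the imprecision of about 30 subjects observed for one week per configuration.

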## PROTOCOL SYNOPSIS

|                   |  |
|-------------------|--|
| Protocol Number   | TP-0009170   |
| Protocol Title    | Control-IQ 2.0 Adult and Adolescent Feasibility Study  |
| Device            | t:slim X2 insulin pump with Control-IQ technology (Control-IQ System). Tandem developed a configurable version of software called Control-IQ Pro which will be used to enable evaluation of new features in this study.  |
| Type of Protocol  | Feasibility Study  |
| Rationale         | The purpose of this study is to obtain preliminary safety and performance data on planned improvements to Control-IQ. Based on data from algorithm simulations and historical customer outcomes on the current algorithm, several new algorithm features have been selected to include in this feasibility study. Outcomes of this study will allow for the determination of the optimal feature set to include in the subsequent clinical trials, and ultimately in the commercial version of Control-IQ 2.0.   |
| Objectives        | 
Primary objective: To demonstrate the safety of the Control-IQ Pro 2.0 System for the management of type 1 diabetes by assessing rates of AEs after using new features.
 
Secondary objective: To further assess the safety of new features that potentially will be added to the current Control-IQ System; specifically, improved time in range (TIR) 70-180 mg/dL, improved time in the tight glycemic range 70-140 mg/dL, and lower median sensor glucose.
   |
| Study Endpoints   | 
1) Primary Safety Endpoints:
 
 
a. Significant hypoglycemia time <54 mg/dL
 
b. Severe hypoglycemia (needing assistance)
 
c. DKA
 
d. Serious Adverse Events
 
 
2) Secondary Safety Endpoints:
 
 
a. Time < 70 mg/dL
 
b. Time > 250 mg/dL
 
c. Overall TIR (70-140 mg/dL)
 
d. Overall TIR (70-180 mg/dL)
 
e. Post-prandial glycemic peak
 
f. 4-hour post meal glucose AUC
 
g. Sensor glucose median and interquartile range
 
h. CGM metrics daytime vs. nighttime
 
 |
| Duration of Study | All subjects will be monitored for approximately 5 weeks after enrolling in the study.   |

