| Statistical Analysis | Descriptive statistics will be used to evaluate rates of AEs as well as glycemic outcomes after using existing Control-IQ system vs. new features. Each subject will use all features and therefore act as his/her own comparator. |
|----------------------|--|

127

128 The study will be conducted and documented in accordance with the US Federal and Local  
129 requirements for post-market human clinical studies, the protocol, and the stipulations of the  
130 clinical trial agreement.

131

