### 2.2 Study Design

This feasibility study is a prospective, crossover study with a 48-hour supervised hospital phase, followed by a 4-week home study with sequential interventions (new features) and remote monitoring. Up to 110 subjects may sign the consent form and be screened, so that a maximum of 90 subjects (up to 30 subjects to wear the study device, and up to 60 personal contacts) may be enrolled. Subjects wearing the device will be both male and female, aged 14 and up, inclusive, who have used Control-IQ in closed-loop at least 80% of the 2-week time period before enrollment. Approximately 5 subjects will be enrolled in the initial 48-hr hospital phase. Approximately 25 additional subjects will be enrolled to participate in the at-home study. Each subject will use all features (current and new) and therefore will act as his/her own comparator. Remote real-time monitoring using the Dexcom G6 app will be required to be shared with their local contact(s) throughout the study, and with study staff for the first 10 subjects. After the first 10 subjects complete the study, required real-time alerts to study providers may be removed for future subjects after sponsor review and approval. Subjects will continue to share with their personal contacts.

The data collected in this study will be directly entered into an electronic data capture system (EDC) using electronic case report forms (eCRFs) when possible. Paper source may also be used. Subject data will include demographics, focused medical history, therapy data, and baseline and follow-up measures.

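### Section 5.1 plans within-subject differences only against a non-randomised baseline; the paired A–B and C–D week differences, each isolating one prescribed setting, are not planned

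*Combined protocol and SAP*

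**What the plan says.** Section 5.1 provides three kinds of output. Event rates "will be reported for baseline and each intervention configuration", and the glycaemic outcomes are summarised by median and interquartile range in the same way, with a day/night sub-analysis. The outcome distributions for baseline and each configuration are shown as boxplots. Finally, "The individual-level difference between each intervention configuration and baseline will also be depicted using boxplots". No difference between two study weeks, no interval and no model appears.

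The synopsis describes the comparison as "glycemic outcomes after using existing Control-IQ system vs. new features". Section 4.4 fixes the comparator: "Data from the 2-week period before enrollment will serve as the baseline pump and CGM data".

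On randomisation, section 4.5.2 introduces Table 4 with "The feature use will be randomized per subject", and the note to the table then says "Each cohort will be randomly assigned the order in which they complete weeks A-D". The number of cohorts and the set of sequences are not given.

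On use of the results, the synopsis rationale says outcomes will allow for the "determination of the optimal feature set to include in the subsequent clinical trials". Section 2.2 adds: "Each subject will use all features (current and new) and therefore will act as his/her own comparator".

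**The concern.** Choosing among features means comparing configurations with each other. The protection from randomised order applies only to comparisons among weeks A to D, whereas every difference in section 5.1 is taken against the period outside that randomisation.

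Baseline precedes all study weeks and runs on the commercial system. Study weeks bring site visits with download review, a routine call about 48 hours after each feature update, re-education when misuse is found, and a required low-alert setting. Closed-loop use in the baseline window is also an eligibility condition, so participants are selected on the comparator period. That could by itself shift later differences, most plainly in time in automation.

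An improvement or deterioration common to all study weeks would appear in all four planned differences and could be credited to a feature. This concerns safety as well as performance, because time below 54 mg/dL is a primary endpoint and section 5.1 summarises it by configuration.

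**Working it through.** The documents state no power, precision or standard deviation, so there is no figure of theirs to reproduce. The check is a count of settings, followed by the precision the added contrasts would have.

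**Step 1. Prescribed settings (Table 4).** Baseline is coded as standard target with Normal-activity auto-bolus on, because section 1.2 says the current system delivers automatic corrections. The instruction not to use Late Bolus is coded as equivalent to its absence at baseline.

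| Period | Target | Normal auto-bolus | Exercise | Eating Soon | Late Bolus |
|---|---|---|---|---|---|
| Baseline | standard | on | standard | none | none |
| A | lower | on | auto-bolus off | before every meal | none |
| B | lower | off | auto-bolus off | before every meal | none |
| C | lower | on | auto-bolus off | as needed | as needed |
| D | standard | on | auto-bolus off | as needed | as needed |

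**Step 2. Settings that differ.**
- Against baseline: A 3 (target, exercise, Eating Soon); B 4 (those three plus Normal auto-bolus); C 4 (A's three plus Late Bolus); D 3 (exercise, Eating Soon, Late Bolus). Counting the change from v1.0 to v2.0 software gives 4, 5, 5 and 4.
- Between weeks: A–B 1 (Normal auto-bolus); C–D 1 (target); A–C 2 (Eating Soon and Late Bolus instructions); A–D 3; B–C 3; B–D 4.

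A–B and C–D are the only single-setting contrasts, and neither is planned.

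**Step 3. What each difference contains.** Suppose effects add. Let T be the lower target, X exercise auto-bolus off, P the as-needed Eating Soon and Late Bolus instructions together, and S the software change plus any study-entry effect common to all weeks. Then, apart from period effects:
- C − baseline = T + X + P + S
- D − baseline = X + P + S
- C − D = T

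For illustration, assume S = 2 points of time in range, T = 1 and the rest zero. Then C − baseline = 1 + 2 = 3, D − baseline = 2 and C − D = 1. Only the last isolates the target. X and S sit in all four baseline differences and cancel in every week-to-week difference, so no comparison in this design isolates either of them.

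**Step 4. Precision of an added paired contrast.** The 95% half-width for a mean paired difference is t(0.975, n − 1) × SD_diff / √n.
- n = 30 (the maximum wearing the device): 2.045/√30 = 0.373 × SD_diff
- n = 25: 2.064/√25 = 0.413 × SD_diff

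SD_diff is not in the documents. Over an assumed 4 to 10 points of time in range, the half-width is 1.5 to 3.7 points for n = 30 and 1.7 to 4.1 points for n = 25. This is the precision of the proposed addition, not a measure of harm from leaving it out. It assumes independent complete pairs, and it is only a rough guide to an interval for a median difference, least of all for a skewed outcome such as time below 54 mg/dL.

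**The case against.** The strongest reply is that the plan does what it sets out to do. The synopsis gives the purpose as preliminary safety and performance data, and section 5.1 speaks of a safety profile by configuration. The remark about the optimal feature set occurs only in the synopsis rationale and looks ahead to later trials. Baseline is the only period on the existing system, so week minus baseline is the comparison the synopsis asks for. All of this stands. A reader might infer that the baseline differences are the wrong analysis and should be demoted; the documents do not support that.

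It is also true that section 5.1 shows all weeks side by side and that the collected data would allow paired contrasts later. So it would be too strong to say that the trial cannot attribute any change to a feature. What is missing is a planned paired estimate. The median of paired differences cannot be recovered by subtracting two reported medians, and contrasts chosen after seeing the data carry less weight.

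A reader might also take A–B and C–D to be unbiased. The text does not establish that. If order is assigned to a few cohorts, week type may be poorly balanced over calendar week, and no washout is described. The contrasts also reflect prescribed use: Eating Soon and Late Bolus are as needed in both C and D, and optional sleep schedules may replace the Normal setting overnight.

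Two further readings go too far. Real-time monitoring by staff does not separate all study weeks from baseline, since it is required only for the first 10 participants. And the own-comparator sentence says that participants use current and new features; it does not claim that each feature is isolated.

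**Conclusion.** The point holds as an inexpensive gap in the analysis plan; it does not invalidate the study. All four planned differences are non-randomised. Each combines three or four prescribed setting changes with the software change and study-entry effects. The two week-to-week differences that isolate one prescribed setting are not planned, although the synopsis says the outcomes will inform the feature set.

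The counts rest on Table 4 and on the baseline coding stated above. The protection that A–B and C–D gain from randomised order depends on how many cohorts and sequences there are, which the documents do not say. Even with these contrasts added, only Normal-activity auto-bolus and the lower target are isolated. Eating Soon and Late Bolus instructions change together, and exercise auto-bolus off and the v2.0 software are constant over weeks A to D. No hypothesis test is called for in a descriptive feasibility study.

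**What to change.** In section 5.1:

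1. Keep the week-minus-baseline differences as the existing-versus-new comparison, and label them non-randomised.
2. Add descriptive within-subject paired differences A–B (Normal-activity auto-bolus) and C–D (lower target), with A–C as a combined contrast of the Eating Soon and Late Bolus instructions. Report each as a median difference with a 95% interval for percentage of time below 54, below 70, above 250, within 70–180 and within 70–140 mg/dL, with adjustment for period.
3. State the limits: exercise auto-bolus off has no comparator among weeks A to D, Eating Soon and Late Bolus cannot be separated, and the contrasts describe prescribed rather than actual use. Word any statement about the feature set accordingly.

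In section 4.5.2, reconcile per-subject randomisation with cohort-level assignment and give the number of cohorts and the sequences. Period balance and the independence of the pairs depend on this.

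The cost is text and a few lines of code, with no new data, visits or change to treatment. The downside is 3 contrasts × 5 outcomes = 15 further intervals, which should be marked descriptive and unadjusted for multiplicity, and a narrower claim about individual features.
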